1.6. Study Rationale

This is the first time OLP-1002 will be administered to humans. The principal aim of this study is to obtain safety and tolerability data when OLP-1002 is administered SC as single and multiple doses to healthy subjects. This information, together with the pharmacodynamic (PD) and pharmacokinetic (PK) data, will help establish the doses and dosing regimen suitable for future studies in patients. The analgesic effects of OLP-1002 on a capsaicin-induced pain model will also be investigated.

1.7. Benefit-risk Assessment

Healthy subjects in the current study will not receive any health benefit (beyond that of an assessment of their medical status) from participating in the study. The risks of participation are primarily those associated with adverse reactions to the investigational medicinal product (IMP), although there may also be some discomfort from collection of blood samples and other study procedures. For subjects in the PD assessment groups in Part A there will be some additional discomfort from the capsaicin test. More information about the known and expected benefits, risks, and reasonably anticipated AEs associated with OLP-1002 may be found in the Investigator's Brochure⁴.

2. OBJECTIVES AND ENDPOINTS

2.1. Objectives

The primary objective of the study is to assess the safety and tolerability of single and multiple SC doses of OLP-1002 in healthy subjects.

The exploratory objectives of the study are to evaluate the PD effect of OLP-1002 following single SC doses in healthy volunteers using a capsaicin pain model, and to monitor the effects of single SC doses of OLP-1002 on cardiac QT interval. Where possible, single and/or multiple subcutaneous dose pharmacokinetics of OLP-1002 in healthy subjects will be determined.

2.2. Endpoints

2.2.1. Primary Endpoints

The primary safety endpoints for this study are as follows:

- incidence and severity of AEs
- vital signs measurements (blood pressure, pulse rate, respiratory rate)
- 12-lead electrocardiogram (ECG) parameters
- incidence of clinical laboratory abnormalities, based on clinical chemistry, hematology, and urinalysis test results
- physical examinations
- injection site assessment.
- demonstrate that exposure to OLP-1002 does not exceed pre-defined exposure limits from non-clinical studies.

2.2.2. Exploratory Endpoints

The following exploratory objectives will be assessed:

- pain intensity and duration will be assessed by AUC, maximum pain intensity (E_{max}), and time of maximum pain intensity (tE_{max}), calculated using a capsaicin-evoked pain model. The exploratory endpoint of secondary hyperalgesia will be assessed by the area of secondary area of hyperalgesia (Part A only).
- continuous (24-hour) ECG monitoring will be recorded in this study and archived for potential future analysis of OLP-1002 effects on the QT interval (Part A).
- heat pain threshold measurements and heat pain tolerance measurements.
- For Part A, the single ascending dose, PK outcome endpoints of OLP-1002 are as follows:

Primary PK

- area under the plasma concentration-time curve (AUC) from time zero to infinity ($AUC_{0-\infty}$) (actual and dose normalized [DN])
- AUC from time zero to the time of the last quantifiable concentration ($AUC_{0-t_{last}}$) (actual and DN)
- maximum observed plasma concentration (C_{max}) (actual and DN)

Secondary PK

- time of the maximum observed plasma concentration (t_{max})
- apparent plasma terminal elimination half-life ($t_{1/2}$)
- For Part B, the multiple ascending dose PK outcome endpoints of OLP-1002 are as follows:

Primary PK:

- AUC over a dosing interval ($AUC_{0-\tau}$) (actual and DN)
- $AUC_{0-\infty}$ (actual and DN)
- C_{max} (actual and DN)

Secondary PK

- minimum observed plasma concentration (C_{min})
- t_{max}
- $t_{1/2}$
- observed accumulation ratio based on $AUC_{0-\tau}$ ($RAAUC_{0-\tau}$)
- observed accumulation ratio based on C_{max} (RAC_{max}).
- Temporal change parameter (TCP)

Other PK parameters may also be added if deemed necessary.

3. INVESTIGATIONAL PLAN

This will be a double-blind, randomized, placebo-controlled, single and multiple SC dose study conducted in 2 parts.

3.1. Overall Study Design and Plan

3.1.1. Part A

Part A will comprise a single-dose, sequential-group design. Overall, 68 healthy subjects will be studied in 11 groups.

Potential subjects will be screened to assess their eligibility to enter the study within 28 days prior to the first dose administration. Potential subjects for Groups A2, A4, A6, A9, A10, and A11 will attend a pre-screening visit for an intradermal capsaicin test ([Section 3.4.2](#)).

Each subject will participate in 1 treatment period only, and will reside at the Clinical Research Unit (CRU) from Day -2 (2 days before dosing) to Day 3. All subjects will return for non-residential visits on Days 4, 7 (± 2 days), 10 (± 2 days), and 14 (± 2 days), and for a poststudy visit on Day 28 (± 2 days).

Based on the ongoing review of the safety and tolerability, additional non-residential visits may be required. The number of additional visits per subject will not exceed 3 and will not extend beyond Day 28 (± 2 days).

Doses will be administered in an escalating manner following satisfactory review of safety and tolerability data up to Day 10 (216 hours postdose) from the lower dose levels. For doses ≥ 12 μg , PK data will also be reviewed up to Day 7 prior to dose escalation.

[figure not shown]
In Part A, Groups A1, A3, A5, A7, and A8 will consist of 4 subjects; 3 subjects will receive OLP-1002 and 1 subject will receive placebo. To assess PD parameters, Groups A2, A4, A6,

A9, A10, and A11 will consist of 8 subjects; 6 subjects will receive OLP-1002 and 2 subjects will receive placebo.

Sentinel dosing will be employed for all groups in Part A. To maintain the blind in a 4-subject group, the first subject will be dosed 48 hours before the second subject, and the second subject will be dosed 48 hours prior to the third and fourth subjects. In PD assessment groups, 2 subjects (1 active: 1 placebo) will be dosed 48 hours before the remaining 6 subjects (5 active: 1 placebo).

An overview of the study design is shown in [Figure 1](#).

Figure 1: Study Schematic (Part A)

Active = OLP-1002; SC = subcutaneous.
Six groups consist of 8 subjects (6 active: 2 placebo); all other groups will consist of 4 subjects (3 active: 1 placebo).

The total duration of study participation for each subject (from Screening through Follow-up visit) is anticipated to be approximately 8 weeks.

3.1.2. Part B

Part B will comprise a multiple-dose, sequential-group study. Overall, 32 subjects will be studied in 4 groups (Groups B1 to B4), with each group consisting of 8 subjects. Up to 2 additional groups (16 subjects in total) may be included for further assessment of safety and tolerability ([Section 3.3](#)).

Potential subjects will be screened to assess their eligibility to enter the study within 28 days prior to the first dose administration. Each subject will participate in 1 treatment period only and reside at the CRU from Day -1 until Day 15.

All subjects will return for non-residential visits on Days 18 (± 2 days), 22 (± 2 days), 25 (± 2 days), and 29 (± 2 days), and for a poststudy visit on Day 57 (± 2 days).

[figure not shown]
In each of Groups B1 to B4, 6 subjects will receive OLP-1002 and 2 subjects will receive placebo. For all subjects, a single subcutaneous dose will be administered on Days 1, 4, 7, 10, and 13. Prior to each dosing occasion a physician will review the available safety and tolerability data from each subject to confirm it is acceptable to continue dosing. The dosing frequency in Part B may be changed following review of data from groups in Part A ([Section 3.4](#)).

Sentinel dosing will only occur in Part B at dose levels where exposure to OLP-1002 at steady state is predicted to exceed exposures that have been shown to be safe and well tolerated in earlier groups in Parts A or B. In the event of sentinel dosing, 2 subjects (1 active, 1 placebo) will be dosed at least 4 days prior to the remaining 6 subjects (5 active: 1 placebo). Safety data for the sentinel subjects from at least 2 additional doses will be reviewed prior to dosing the remaining subjects (i.e. sentinel subjects' safety data after doses 1 and 2 will be reviewed prior to the remaining subjects receiving dose 1). In addition, safety data from each subject will be reviewed by a physician prior to each dose to approve continued dosing.

Doses will be administered in an escalating manner following satisfactory review of safety, tolerability, and PK data up to Day 22 (216 hours post-final dose) from the lower dose levels. Part B may start after a review of the safety, tolerability, and available PK for Groups A1 to A6. The total daily dose administered will not exceed the highest single dose given in Part A.

An overview of the study design is shown in [Figure 2](#).

Figure 2: Study Schematic (Part B)

Active = OLP-1002; SC = subcutaneous; TBC = to be confirmed.
All doses will be confirmed based on results of Part A and previous groups in Part B.
Groups B5 and B6 will be included if required.

The total duration of study participation for each subject (from Screening through Follow-up visit) is anticipated to be approximately 12 weeks.

A Schedule of Assessments is presented in [Appendix 6](#).

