7.3.2. Clinical Laboratory Evaluations

Blood and urine samples will be collected for clinical laboratory evaluations (including clinical chemistry, hematology, urinalysis, and serology) at the times indicated in the Schedule of Assessments in [Appendix 6](#). Clinical laboratory evaluations are listed in [Appendix 2](#). Additional clinical laboratory evaluations will be performed at other times if judged to be clinically appropriate or if the ongoing review of the data suggests a more detailed assessment of clinical laboratory safety evaluations is required.

Subjects will be asked to provide urine samples for drugs of abuse screen and cotinine test, and will undergo an alcohol breath test at the times indicated in the Schedule of Assessments in [Appendix 6](#). For all female subjects, a follicle-stimulating hormone (FSH) test and pregnancy test will be performed at the times indicated in the Schedule of Assessments in [Appendix 6](#).

An Investigator (or designee) will perform a clinical assessment of all clinical laboratory data.

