Appendix 3: Total Blood Volume

The following blood volumes will be withdrawn for each subject.

Part A

	Volume per blood sample (mL)	Maximum number of blood samples	Total amount of blood (mL)
Pharmacokinetic analysis	4	19	76
Clinical laboratory evaluations (excluding serology)	7.5	6	45
Serology	3.5	1	3.5
Total:			124.5

Part B

	Volume per blood sample (mL)	Maximum number of blood samples	Total amount of blood (mL)
Pharmacokinetic analysis	4	29	116
Clinical laboratory evaluations (excluding serology)	7.5	10	75
Serology	3.5	1	3.5
Total:			194.5

If extra blood samples are required, the maximum blood volume to be withdrawn per subject during the study will not exceed that donated during a standard blood donation (approximately 500 mL).

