^a Female subjects only; a positive urine pregnancy test result will be confirmed with a serum pregnancy test.

^b All times are relative to dosing with OLP-1002.

^c Continuous ECG recording may begin at approximately 25 hours before dosing to allow for checks to be completed prior to the first extraction timepoint and will continue for 24 hours postdose, ie, until after the last timepoint for ECG extraction (24 hours postdose). At timepoints for ECG extractions, subjects will be supinely resting for a total of 15 minutes (10-minute supine rest period, 5-minute extraction). Data will be archived for potential future analysis and will not be available for review during the study.

^d Pharmacodynamic assessment groups only.

^e PK analysis in Part A will initially only be conducted for groups receiving $\geq 12 \mu\text{g}$ OLP-1002, with retrospective analyses of samples from lower dose groups occurring in the event of PK data being quantifiable at doses $\geq 12 \mu\text{g}$ and if supported by bioanalytical stability data.

Study Plan – Part B (Multiple Dose)

	Screening	Day -1	Days 1-15	Day 18 (± 2 days)	Day 22 (± 2 days)	Day 25 (± 2 days)	Day 29 (± 2 days)	Poststudy (Day 57 ± 2 days)
Inclusion/exclusion criteria	X							
Demographic data	X							
Medical history	X							
Urine drugs of abuse screen	X	X						
Alcohol breath test	X	X						
Cotinine test	X	X						
Serology	X							
FSH and serum pregnancy test ^a	X							
Urine pregnancy test ^a		X			X		X	X
Informed consent	X							
Study residency:								
Check-in		X						
Check-out			Day 15 (48 hours postdose)					
Non-residential visit	X			X	X	X	X	X
Study drug administration:			Days 1, 4, 7, 10, and 13					
Safety and tolerability:								
Adverse event recording	X	X	Ongoing	X	X	X	X	X
Concomitant medication recording	X	X	Ongoing	X	X	X	X	X
Supine blood pressure, pulse rate, respiratory rate, and body temperature	X		Day 1: predose, 1, 2, 4 and 8 hours postdose Day 2, Day 4 (postdose), Day 5, Day 7 (postdose), Day 9, Day 10 (postdose), Day 12, Day 13: predose, 1, 2, 4 and 8 hours postdose, and Day 15	X	X	X	X	X

	Screening	Day -1	Days 1-15	Day 18	Day 22	Day 25	Day 29	Poststudy (Day 57 ± 2 days)
Heat pain threshold test (heat pain threshold and heat pain tolerance)	X		Day 1 and Day 13: predose, 1, 2, 4, 8, 24 hours postdose					

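### The Part B laboratory sample after the fifth dose is scheduled for Day 17, two days after check-out, and is tied to neither Day 15 nor the Day 18 visit

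*Protocol*

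**What the plan says.** All references are to the current protocol text (Version 5).

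- **Dosing.** Section 3.1.2: "a single subcutaneous dose will be administered on Days 1, 4, 7, 10, and 13". Dose 5, the last, is therefore on Day 13.
- **Residence.** Section 3.1.2: "Each subject will participate in 1 treatment period only and reside at the CRU from Day -1 until Day 15". The check-out row of the Part B schedule in Appendix 6 agrees: "Day 15 (48 hours postdose").
- **Return visits.** Section 3.1.2: "All subjects will return for non-residential visits on Days 18 (± 2 days), 22 (± 2 days), 25 (± 2 days), and 29 (± 2 days"), followed by a poststudy visit on Day 57 (± 2 days).
- **Laboratory row.** In the Part B schedule, clinical chemistry, haematology and urinalysis are marked at Screening and Day -1. They are then listed for Days 2, 5, 9, 12 and 17 inside the column headed Days 1-15, and marked again at Days 22, 29 and 57. The cells for Day 18 and Day 25 are blank.
- **Blood volume.** Appendix 3 allows Part B 10 laboratory samples of 7.5 mL, 75 mL in all, excluding serology.
- **Escalation review.** Section 3.1.2 bases the next Part B dose on safety, "tolerability, and PK data up to Day 22 (216 hours post-final dose) from the lower dose levels".

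**The concern.** Day 17 cannot belong to the column that contains it. By then the subject has left the unit, and no visit carries that day number. Neither of the two neighbouring occasions when the subject is on site, check-out on Day 15 and the Day 18 visit, has a laboratory mark. A site that sees the subject on nominal Day 18 and works down the Day 18 column draws no safety laboratory sample. It also has no prompt to ask for the overnight fast that Section 6.2 requires before such samples.

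Incidence of clinical laboratory abnormalities is a primary safety endpoint (Section 2.2.1), and the liver criterion for stopping escalation (Section 3.7) rests on these samples. Doses 1 to 4 are each followed by a laboratory test while the subject is resident. Dose 5 is not. If the Day 17 sample is missed, a liver, renal or haematological change that appears and resolves in the first week or so after the last dose would go unseen. The same schedule applies to every Part B subject: 32 in Groups B1 to B4, and up to 32 + 16 = 48 if Groups B5 and B6 are added.

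**Working it through.** **1. Is Day 17 a planned sample?** Count the Part B laboratory row: Screening, Day -1, Days 2, 5, 9, 12, 17, 22, 29 and 57. That is 10 samples, and 10 × 7.5 mL = 75 mL. This reproduces the Appendix 3 figure. Without Day 17 the count would be 9. The sample is intended.

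**2. How long after the preceding dose is each test?** Lag = (test day − dose day) × 24 h, with doses on Days 1, 4, 7, 10 and 13.

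| Test day | Preceding dose | Lag | Subject on site? |
|---|---|---|---|
| 2 | 1 (Day 1) | 24 h | Resident |
| 5 | 2 (Day 4) | 24 h | Resident |
| 9 | 3 (Day 7) | 48 h | Resident |
| 12 | 4 (Day 10) | 48 h | Resident |
| 17 | 5 (Day 13) | 96 h | Checked out on Day 15; no visit named Day 17 |
| 22 | 5 (Day 13) | 216 h | Return visit |

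No resident laboratory test follows dose 5.

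**3. Do the visit windows rescue the sample?** Day 18 ± 2 covers Days 16 to 20, which is (16 − 13) × 24 = 72 h to (20 − 13) × 24 = 168 h after dose 5. Day 17 is one of those five days, so attendance on Day 17 is permitted but is not the nominal day. Day 22 ± 2 covers Days 20 to 24, which is 168 h to 264 h after dose 5.

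**4. What do comparable rows do?** The ECG and injection-site rows have the same later pattern as the laboratory row (blank at Day 18, marked at Day 22), but their in-unit lists end on Day 15. Vital signs and a PK sample are also taken on Day 15. In Part A the laboratory sample is at 48 h, which is the time of check-out. The Part B laboratory row is the only one of these with nothing at check-out.

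**5. How much exposure is involved?** Assume one-compartment decline with the 180-h half-life in Sections 3.4 and 3.5.2 and the 72-h dosing interval. The ratio per interval is r = 2^(−72/180) = 0.758. Exposure just after each dose, relative to dose 1, is the running sum 1 + r + r² + …, giving 1, 1.76, 2.33, 2.77 and 3.10.

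- Dose 5 against dose 4: 3.10 / 2.77 = 1.12, about 12% higher.
- Fraction of the post-dose-5 level remaining: 2^(−168/180) = 52% at 168 h, 2^(−216/180) = 44% (0.435) at 216 h and 2^(−264/180) = 36% at 264 h.
- Level at 216 h relative to the first-dose peak: 0.435 × 3.10 = 1.35.

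**The case against.** The strongest reply is that the protocol does require a Day 17 sample, and a site that reads the laboratory row would simply book the Day 18 visit on Day 17, as the window allows. The entry is not a PDF artefact. It also stands in the schedules of the older protocol versions in the same file, and the amendment summary records it as a deliberate change to the laboratory timepoints. Section 7.3.2 adds flexibility: "Additional clinical laboratory evaluations will be performed at other times if judged to be clinically appropriate". Section 7.3 lets safety timepoints be adjusted on ongoing review. Other monitoring after dose 5 is unaffected: vital signs on Days 13, 15 and 18, ECG and injection site on Days 13 and 15, and continuous adverse event recording.

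Much of this stands, and it rules out some stronger readings.

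- A reader might infer that no laboratory test can be attended between dose 5 and Day 22. That is not so: Day 17 lies inside the Day 18 window, and the Day 22 visit can be held from Day 20.
- A reader might infer that the escalation review would lack laboratory data after dose 5. That is not so: Day 22 carries a laboratory mark, and the review runs to Day 22.
- A reader might infer that the highest exposure goes unmonitored. On the model above, dose 5 is only about 12% above dose 4, which has a resident 48-h sample, and the level at 216 h is still above the first-dose peak.
- The withdrawal criteria have little to act on here, because no dose follows dose 5.

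The reply does not remove the contradiction. Following the visit columns and following the laboratory row lead to different conduct unless the visit falls on one particular day out of five. The extra tests in Section 7.3.2 depend on a clinical judgement or a signal in the data, so they cannot stand in for a scheduled test meant to find silent changes.

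**Conclusion.** The schedule is wrong as written. A planned sample, the only early laboratory test after the last Part B dose, sits in a column it cannot belong to and is attached to no visit. If the Day 18 visit is not held on Day 17, the first marked laboratory test after dose 5 is nominally at 216 h (168 to 264 h with the window). For doses 1 to 4 it comes at 24 to 48 h. What could be lost is a transient change that resolves before about Day 22. A change that persists would still be seen at Day 22 and would reach the escalation review.

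The scheduling conclusion rests only on the protocol's own day numbers, windows and sample count. The exposure figures assume one-compartment decline with the predicted 180-h half-life and serve only to show scale. How often the sample would be missed depends on how the site books the Day 18 visit, which the protocol does not say. This is more than a typographical matter because a primary safety endpoint and the liver stopping criterion draw on the row, but it does not leave the fifth dose without laboratory follow-up.

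**What to change.** In the Part B laboratory row of Appendix 6, replace Day 17 with Day 15, at check-out. The sample then falls (15 − 13) × 24 = 48 h after dose 5, matching the lag after doses 3 and 4 and the check-out sample in Part A, on a day when blood is already drawn for PK.

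Alternatively, remove Day 17 from the list and mark the laboratory row at the Day 18 (± 2 days) visit. That places the sample 72 to 168 h after dose 5, which is later and less uniform, and subjects would have to be told to fast before that visit.

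Either change is one schedule entry in the next amendment. The count stays at 10 samples and 75 mL, with no added visit and no change to Appendix 3.

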3.4.1. Dose Interval

Following thorough review of all available nonclinical data (pharmacological and toxicological), dosing in Part A for groups consisting of 4 subjects will be such that there will be 48 hours between the first and second subjects, and 48 hours between the second and remaining 2 subjects in each group. For groups in Part A consisting of 8 subjects, 2 subjects (1 active: 1 placebo) will be dosed 48 hours prior to the remaining 6 subjects.

In Part B, sentinel dosing will be used in groups where exposure to OLP-1002 at steady state is predicted to exceed exposures that have been shown to be safe and well tolerated in earlier groups in Parts A or B. When used, two subjects (1 active; 1 placebo), will be dosed 4 days prior to the remaining 6 subjects (5 active; 2 placebo). The 2 sentinel subjects will always be 2 doses ahead of the remaining subjects (ie. sentinel subjects will receive dose 2 before the remaining subjects receive dose 1). Subjects in groups where exposure is not predicted to exceed that tested in Part A will be dosed on the same day. Accumulation of OLP-1002 is expected following multiple doses, based on the preclinical data, and will be taken into account when determining the doses for Part B (see [Section 3.5.3](#)). If it is not possible to quantify exposure it will be assumed that multiple dosing results in a 4-fold accumulation based on the predicted $t_{1/2}$ of 180h.

In Parts A and B, there will be a minimum interval of a 10-minute gap between dosing subjects (when dosed on the same day). Continuation to dose the remaining subjects in a group will be at the Investigator's discretion.

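### The Part B sentinel rule is stated inconsistently: a 4-day lead satisfies the explanations given at a 72 h dosing interval, but not the headline wording, and at 96 h it satisfies neither

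*Protocol*

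**What the plan says.** Two sections of the current protocol (Version 5) describe sentinel dosing in Part B. Each makes a headline statement and then an explanation introduced by *i.e.*

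- **Section 3.1.2, lead and split:** "2 subjects (1 active, 1 placebo) will be dosed at least 4 days prior to the remaining 6 subjects (5 active: 1 placebo").
- **Section 3.1.2, review:** the headline is "Safety data for the sentinel subjects from at least 2 additional doses will be reviewed prior to dosing the remaining subjects". The explanation is "sentinel subjects' safety data after doses 1 and 2 will be reviewed prior to the remaining subjects receiving dose 1".
- **Section 3.4.1, lead and split:** "will be dosed 4 days prior to the remaining 6 subjects (5 active; 2 placebo").
- **Section 3.4.1, ordering:** the headline is "The 2 sentinel subjects will always be 2 doses ahead of the remaining subjects". The explanation is "sentinel subjects will receive dose 2 before the remaining subjects receive dose 1".

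On the schedule, Section 3.1.2 states that "a single subcutaneous dose will be administered on Days 1, 4, 7, 10, and 13", and adds that the frequency may change after Part A data are reviewed. Section 3.5.2 anticipates an interval of 72 or 96 hours. Neither sentinel section sets a minimum observation time after sentinel dose 2.

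**The concern.** The headline statements and their explanations do not describe the same schedule. Data from two additional doses, read naturally as two doses beyond the first, means sentinel doses 2 and 3; the explanation says doses 1 and 2. A lead that is always two doses is a stronger condition than having sentinel dose 2 come before the others' dose 1. The lead is a minimum in one section and a fixed figure in the other, and the two sections give different allocations for the same six people.

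This matters because Part B uses sentinels only where predicted steady-state exposure goes beyond what earlier groups have tolerated. Section 3.5.3 shows how that could arise: it allows Group B4 at 20 µg to be dosed after the escalation meeting for Group A9, with a predicted AUC of 3.15 ng.h/mL against 1.673 for A9 (3.15 / 1.673 = 1.88-fold). In such a group, the rule decides what is known about repeat dosing in one active subject before five more are exposed. Two sites, or two physicians at one site, could follow different sentences and run different schedules.

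**Working it through.** **Inputs.** Sentinel doses on Days 1, 4, 7, 10, 13 (Section 3.1.2), so every gap is 3 days = 72 h. Lead L = 4 days (fixed in Section 3.4.1, minimum in Section 3.1.2). Alternative interval 96 h (Section 3.5.2). All times are nominal.

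**Step 1: the explanations at 72 h.** Sentinel dose 2 falls at 72 h. With L = 4 days the others' dose 1 falls at 4 × 24 = 96 h, on sentinel Day 5. Sentinel dose 2 therefore comes first, with 96 − 72 = 24 h of observation after it. Both explanations are met. They need only a lead of more than 3 days.

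**Step 2: the headline statements at 72 h.** The others' doses fall on the sentinel dosing days plus L. At each of the others' five doses, count sentinel doses given minus others' doses given, just before and just after. A same-day sentinel dose counts only in the just-after column.

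| Lead (days) | Others' doses, on sentinel Days | Ahead just before doses 1–5 | Ahead just after doses 1–5 | Hours since sentinel doses at others' dose 1 |
|---|---|---|---|---|
| 4 | 5, 8, 11, 14, 17 | 2, 2, 2, 2, 1 | 1, 1, 1, 1, 0 | 96 (dose 1), 24 (dose 2) |
| 5 | 6, 9, 12, 15, 18 | 2, 2, 2, 2, 1 | 1, 1, 1, 1, 0 | 120, 48 |
| 6 | 7, 10, 13, 16, 19 | 2, 2, 2, 2, 1 | 2, 2, 2, 1, 0 | 144, 72, 0 (dose 3) |
| 7 | 8, 11, 14, 17, 20 | 3, 3, 3, 2, 1 | 2, 2, 2, 1, 0 | 168, 96, 24 (dose 3) |

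With a 4-day lead the sentinels drop to one ahead when the others are dosed on sentinel Day 5, and return to two ahead at sentinel dose 3 on Day 7. That is 48 h of a 72 h cycle at one ahead. A lead of at least 6 days is needed to remain two ahead until sentinel dosing ends on Day 13. For two doses beyond the first (doses 2 and 3) to precede the others' dose 1, the lead must exceed 6 days, because sentinel dose 3 is itself at 144 h.

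**Step 3: the 96 h interval.** Sentinel dose 2 falls at 96 h, and a 4-day lead puts the others' dose 1 at 96 h. The difference is 0 h, so at nominal times there are no data after sentinel dose 2 to review and neither explanation is met. This applies whenever the first interval is 96 h, whether or not later intervals are the same.

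**Step 4: the split.** Section 3.4.1 gives 5 + 2 = 7 for 6 subjects. Adding the sentinel pair gives 6 active and 3 placebo, 9 in all, against the 6 active and 2 placebo in a group of 8 set by Section 3.1.2. The 5 + 1 in Section 3.1.2 adds up.

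**The case against.** The best defence is that each headline is followed by its own definition, and that the two definitions agree: the sentinels have had dose 2 before anyone else has dose 1. A 4-day lead at 72 h delivers that. The sentinels are also two doses ahead at the moment each of the others' doses 1 to 4 is decided, and *additional* could mean additional to what the others have received. Section 3.1.2 sets a floor, so a longer lead is allowed, and review after dose 2 is a separate condition that a site must also meet. A physician reviews each subject before every dose. All of this stands, and it rules out a stronger reading that might be inferred, namely that a 4-day lead makes the rule impossible to follow.

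Two further inferences are tempting and also go too far.

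- **Laboratory data.** Under a 4-day lead, the next scheduled laboratory sample after sentinel dose 2 is on Day 5, the day the others are dosed. A reader might conclude that the sentinel review is defective for lack of that result. No text makes it part of the review, which is of safety data generally. Appendix 6 schedules vital signs, ECG, injection-site assessment and a symptom-directed examination on Day 4, and Section 7.3.2 permits extra laboratory tests. What is missing is a statement of whether the Day 5 result counts.
- **Exposure.** With the protocol's 180 h half-life and simple superposition, r = 2^(−72/180) = 0.758. Accumulation is then 1.758 after dose 2 and 3.097 after dose 5, a ratio of 57%. This does not measure the inconsistency: it follows from reviewing doses 1 and 2, which the protocol states openly. It would be the same with a 6-day lead, where sentinel dose 3 falls at the same nominal time as the others' dose 1. No section sets a target fraction.

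The defence does not cover the fixed 4 days in Section 3.4.1, the word *always*, the 96 h interval or the 5:2 split.

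**Conclusion.** The rule is wrong as written and should be corrected. At 72 h, the explanations need a lead of just over 3 days. The headline wording, read literally, needs at least 6 days to stay two doses ahead during sentinel dosing, and more than 6 for two doses beyond the first. At 96 h, the fixed 4-day lead leaves 0 h after sentinel dose 2. The inconsistency therefore changes what a site would do in the groups where sentinels are required.

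The 24 h figure belongs to a lead of exactly 4 days at 72 h; under Section 3.1.2 it is a minimum, not the expected value. The results assume nominal dosing times at the same clock hour. They say nothing about which lead is clinically right.

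**What to change.** Reconcile Sections 3.1.2, 3.4.1 and 3.5.2 into one rule, stated once and cross-referenced:

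- state which sentinel doses must be completed and reviewed before the remaining subjects receive their first dose;
- derive the lead from that requirement and the dosing interval actually used, so that it remains valid if the interval changes;
- say whether the Day 5 laboratory result is part of the review;
- remove the headline statements that do not fit, and make the lead either a minimum or a fixed figure in both sections;
- correct the 5:2 split in Section 3.4.1.

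The number of doses and days is for the sponsor and investigator to choose. The cost is wording in two or three sections. If a longer reading is kept, it adds at most a few days to each sentinel group.
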